## **Ethics**

Ethics approval from the HREC at Avondale College of Higher Education will be obtained prior to study commencement. Where a participating hospital requires local HREC and/or site specific authorisation, this will be obtained prior to study commencement. The project manager will submit and, where necessary, obtain approval from each HREC for all subsequent protocol amendments, once approved by the study investigators. The project manager will also notify the HREC of deviations from the protocol or serious adverse events occurring at the hospital in accordance with local procedures. The investigators and project manager will be responsible for adhering to ethics committee requirements throughout the study.

## ***Online survey and focus group***

Informed consent will be obtained from the participants in both the online survey and focus group. For the survey, study information and consent will be at the beginning of the survey. It will not be possible to progress to the questions in the survey, without having provided consent. No identifiable or re-identifiable data will be collected. For the focus group, consent will be obtained at the beginning of the session. Only participants who sign the handed out consent form will proceed to participate in the focus group.

### *Catheter data*

For this study, individual patient consent will not be obtained. There is no patient intervention, simply a collection of existing data, provided to researchers in a de-identified format. Researchers have at no stage any patient contact or access to patient information. The timing of consent can be problematic in stepped wedged designs, as evidenced by a study, in which the Research Ethics Committee considered it was reasonable not to obtain informed consent at the start of the study (when care as usual was delivered).

A request for waiver of informed consent will be sought from the HREC, using the criteria for waivering of consent as stated in the National Statement on Ethical Conduct in Human Research (NHMRC). The following points will be made to support this waiver:

- Involvement in the research carries no more than low risk for participants. The insertion of a urinary catheter will occur in patients, regardless of whether they are involved in this research or not. This is the decision of the treating clinician. Placement of the CATH TAG on catheters does not involve a change in existing procedures but rather involves an addition to existing procedures. The CATH TAG serves to prompt responsible nurses to revise catheters still in place after 20 hours. The CATH TAG will not affect the decision if the catheter has to be removed or will stay in place. This remains the decision of responsible nurses and clinicians. No harm or discomfort is anticipated with the implementation of the CATH TAG. However, should patients show signs of discomfort by the CATH TAG, the CATH TAG will be removed immediately.
- As there is no anticipated harm or risk for use of the CATH TAG, during consent we would be required to counsel patients on a risk that is negligible and potentially distract them from the wider medical issues resulting in the need for catheterisation in the first instance. Such counselling would result in a significant administrative burden, for no perceived value given the low risk involved. There is a prospect of causing undue harm if the need to uphold the autonomy of each individual were to be exercised to the fullest extent. This harm (maleficence) is considered to be higher than the harm arising from potential misuse of patients' personal information. For example, consent would require holding additional identifiable information about the patient e.g. name and date of birth.
- It is impracticable to obtain consent for a number of reasons:
  - Urinary catheters are inserted in a variety of settings within a hospital. It would not be possible for researchers to determine or access patients (participants) who are about to receive a catheter. Similarly, urinary catheters are inserted by clinicians (nurses and

medical doctors) at any time of the day, it is not possible for all staff involved in catheterisation to be reached.

- Obtaining consent would require researchers to have access to a higher level of patient history and personal data.
- The clinician obtains consent for the insertion of a catheter, as part of usual medical treatment/processes, following local hospital policy.
- Urinary catheters are often inserted at a time where the patient (participant) requires urgent medical or surgical attention. Obtaining consent related to this study may delay the insertion of a catheter, compromising patient (participant) harm and increasing the risk of harm to patients.
- Retrospective consent, i.e. an approach that would result in the researchers retrospectively contacting participants to seek permission to access their medical records would raise the following ethical issues:
  - There would be considerable loss of participants included in the study as there is no system in place to identify which patients had a catheter inserted while in hospital. As such, the research could not be conducted. If a system were established, it would be administrative in nature. Further it would require the researchers to have access data of potential participants so they could be contacted. These details would include data such as names and postal addresses – information the researchers are not required to have as part of the proposed study design.
  - There would be the risk of contacting patients who underwent significant harm whilst in hospitals, suffered a traumatic event or may have passed away. The process of acquiring informed consent retrospectively would potentially result in increased harm for those participants.
- There is no known or likely reason for thinking that participants would not have consented if they had been asked as there is no risk involved and no patient intervention.
- The clinician will be following local hospital policy regarding the insertion of a catheter.
- There is no variation of care, rather an addition to existing policies, unless contra-indicated.
- De-identified patient data is being collected by the researchers, no identifiable or re-identifiable information is being collected.

In addition to the NHMRC National Statement on Ethical Conduct in Human Research, there is the Ottawa Statement on the Ethical Design and Conduct of Cluster Randomized Trials. This statement makes the following recommendation with respect to waiver of consent:

*“Recommendation 6: A REC may approve a waiver or alteration of consent requirements when (1) the research is not feasible without a waiver or alteration of consent, and (2) the study interventions and data collection procedures pose no more than minimal risk.”* 

- As described in the preceding sections, consent is not feasible and the intervention is no more than minimal risk.

### **Data management**

The project manager, chief investigator and study staff are responsible for maintaining a comprehensive and centralised filing system of all study-related (essential) documentation, suitable for inspection at any time by the approving HREC or applicable regulatory authorities.

Documentation will be stored on a network storage service, which has an automated back-up system. Data will be shared via a password protected file storage server at Avondale College. Data will be stored in de-identifiable format.

## Timelines

The table below summarises the proposed timelines for this project.

**Table 4. Project timeline**

Activity	2017						2018												2019					
	J	A	S	O	N	D	J	F	M	A	M	J	J	A	S	O	N	D	J	F	M	A	M	J
Appointment and commencement of project manager	X	X																						
Finalise protocol, recruitment of sites and ethics approval at administering organisation	X	X																						
Clinical trial registration and submission of protocol	X	X																						
Site specific approvals/authorisation and local ethics approvals		X	X																					
Study commencement and data collection						X	X	X	X	X	X													
Survey											X													
Data analysis Manuscript writing											X	X	X	X	X	X								
Focus group													X											
Peer review journal publication(s) submission Dissemination and translation into practice activities															X	X	X	X	X	X	X			

## **Resourcing and Budget**

The project is funded from an industry grant. In-kind support is provided by Avondale College and higher education institutions with which the Chief Investigators are affiliated. CI [name] will take responsibility for the budget and allocation of resources, with support from the Project Manager and Project Officer.

## **Monitoring**

The investigators and research team, led by the project officer, will monitor data collection processes for each ward or unit at least weekly. Data will be reviewed on a weekly basis to ensure correct collection of the control and intervention data sets. Support (site visits, video conference, telephone and email contact) will be provided by the project manager as required during the initial parts of the control and intervention phases to check core trial processes and maintain data quality.

## ***Adverse event reporting***

The project manager is responsible for ensuring that all adverse events observed by the investigator/s, research team or reported by wards or units are collected and recorded in the source documents. The project manager will notify the approving ethics committee of serious adverse events occurring at any of the sites. Adverse events could require reporting as per hospital specific policy.

## ***Incident monitoring and reporting***

The project manager is responsible for ensuring that all incidents observed by the investigator/s, research team or reported by wards or units are collected, reviewed and recorded in the source documents. Incidents could require reporting as per hospital specific policy and/or notification to the approving ethics committee.

## **Intellectual property**

All Intellectual Property generated through the project will be managed in accordance with Avondale College's Intellectual Property Policy.

Intellectual property that pertains to the electronic reminder system resides with CATH TAG.

## **Safety**

The following will be used to evaluate the safety of staff involved in the study:

- adverse events report

- incident monitoring.

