### ***Outcomes measures***

There are two objectives for this study, (1) determining the effectiveness of the intervention and (2) the effect of the intervention on nurses' ability to deliver patient care. A summary of the objectives' key outcome measures is shown in Table 2.

Table 2. Key outcome measures

Objective 1
 
To determine the efficacy of an electronic reminder system in reducing urinary catheter usage.
	Primary outcome	1. Urinary catheter device utilization ratio (number of urinary catheter-days divided by the number of patient-days)
	Secondary outcome(s)	
1. The number of cases of catheter associated asymptomatic bacteriuria (CA-ASB) per 100 catheter days.
 
2. The number of urinary catheters inserted per 100 patient admissions

Objective 2
 
To determine whether the CATH TAG has an effect on nurses' ability to deliver patient care.
	Primary outcome	1. Perceptions of nurses about ease of use of the CATH TAG
	Secondary outcomes	
2. Perceptions of nurses about effectiveness of the CATH TAG
 
3. Changes in ownership or interest by patients in catheter management
 
4. Barriers to the CATH TAG working successfully in varied types of patients

Note: CA-ASB = catheter associated asymptomatic bacteriuria; CAUTI = catheter associated urinary tract infection

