## ***Data collection***

*Objective 1: To determine the efficacy of an electronic reminder system in reducing urinary catheter usage*

Data will be collected by a specific staff member at the hospital, supported by the research team. Where data collection results in an increase in workload for the hospital staff (e.g. not part of usual practice), the research team will provide additional resources in the form of funding to account for additional hours for existing staff members or employment of new staff members for the purpose of data collection. The research team will provide the hospital staff member(s) with training about the project, data collection processes and data collection tools, as well as ongoing on-site and telephone support. For the purpose of this protocol, the dedicated hospital staff member(s) will be referred to as hospital personnel.

The figure below (Figure 2) summarises the data collection process with further details provided below.

*Figure 2.* Overview of the data collection process

Hospital personnel will prospectively collect data five days a week on participating hospital wards, during both control and intervention periods. Hospital personnel will visit inpatient areas and patients who receive an indwelling urinary catheter will be identified and followed-up until discharge or catheter removal. Hospital personnel will check that a CATH TAG has been attached to every catheter, on wards that have crossed over to the intervention. The following information will be collected: hospital number, age, sex, date of admission, date and time of catheter insertion, reason for censoring follow-up, date of discharge or catheter removal, designation of person

inserting the catheter, ward and allocation to control or intervention ward. A review of microbiology results will be undertaken by the hospital personnel for each person who receives a catheter and has a urinary sample taken. If a person has a positive urine culture after catheterisation and prior to removal, the following will be collected: data of specimen collection, organism(s) isolated, colony forming units, white cell count.

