### ***Data analysis***

*Objective 1: To determine the efficacy of an electronic reminder system in reducing urinary catheter usage.*

The primary outcome measure is the duration of catheterisation, and the study aims to evaluate the effect of the intervention. The analysis will be performed using the generalised estimating equations, using the duration of catheterisation as the dependent variable and intervention as the independent variable. Duration of the intervention will be treated as a confounding variable. It is anticipated that duration of catheterisation will be normally distributed, but exploratory analyses (and where necessary transformation) will be performed. Robust standard errors will be used to adjust for correlation at ward level and autocorrelation in time. There is no expected delay in the effect of the intervention on the outcome.

*Objective 2: To determine whether the CATH TAG has an effect on nurses' ability to deliver patient care.*

Survey:

Data from the anonymous online survey will be analysed using SPSS. It is anticipated that data will be normally distributed but exploratory analyses will be performed, including testing of assumptions of linearity, homoscedasticity, multicollinearity and normality of errors and if necessary transformation of data. Validity and reliability will be examined. Subsequently a general satisfaction score and individual satisfaction scores for the four dimensions of nurses' experiences with the CATH TAG (Ease of use, Effectiveness, Changes in ownership, Barriers) will be calculated. Regression analysis will be conducted to determine if the duration of the intervention or the ward nurses primarily work on had an effect on nurses' experiences with the CATH TAG.

Any problems reported in the open questions will be taken into the focus group to be discussed and subsequently analysed qualitatively (see below).

Focus group:

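### The duration analysis has no rule for a second catheter in the same patient, so a reversed removal can score as benefit, and no outcome isolates re-insertion

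*Protocol*

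**What the plan says.** All references are to the protocol.

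- **Mechanism (Background).** The red light is the nurse's cue to reassess the catheter and take it out if it is no longer needed.
- **Follow-up (Data collection).** "patients who receive an indwelling urinary catheter will be identified and followed-up until discharge or catheter removal".
- **Catheter-days (Data collection, before Table 3).** These are counted for each patient from insertion to removal. Nothing is said about a patient who receives a second catheter.
- **Analysis (Data analysis, Objective 1).** "The primary outcome measure is the duration of catheterisation". It is the dependent variable of the only Objective 1 model described. The text does not say whether the unit is the catheter, the first episode or the patient.
- **Outcomes (Table 2).** The primary outcome listed is "Urinary catheter device utilization ratio (number of urinary catheter-days divided by the number of patient-days". The second secondary outcome is "The number of urinary catheters inserted per 100 patient admissions". No outcome concerns re-insertion.
- **Safety.** "The following will be used to evaluate the safety of staff involved in the study": an adverse events report and incident monitoring.
- **Adverse event reporting.** The project manager ensures that "all adverse events observed by the investigator/s, research team or reported by wards or units are collected and recorded", and "The project manager will notify the approving ethics committee of serious adverse events occurring at any of the sites". The section on incidents is equally broad. Neither is limited to staff.
- **Ethics, Catheter data.** "No harm or discomfort is anticipated with the implementation of the CATH TAG". Researchers receive de-identified data.
- **Items recorded (Table 3).** Hospital number, insertion and removal dates and times, and the reason for censoring. There is no re-insertion item.

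**The concern.** An intervention that prompts removal can do two things: take out catheters that are no longer needed, and take out some that then have to go back. A sound outcome credits the first and not the second. As written, follow-up ends at removal and the model uses duration. The days on a re-inserted catheter may therefore be dropped, or may enter as a further short duration. Either way the intervention phase looks better.

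Two things are at stake. One is a bias in a known direction, towards the tag, in the only Objective 1 model the protocol describes. The other is a patient-safety comparison between phases that the trial could make largely from items it already records, but does not plan.

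**Working it through.** The protocol states no figure on this point, so there is none to reproduce. The check compares how each possible score treats a reversed removal.

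**Step 1: one patient.** Suppose a 6-day catheterisation becomes 3 days, removal, re-insertion and 3 more days.

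| Score | Before | After |
|---|---|---|
| Duration to first removal | 6 | 3 |
| Mean duration per catheter | 6 | (3 + 3)/2 = 3 |
| Total catheter-days per patient | 6 | 6 |
| Numerator of the utilisation ratio | 6 | 6 |
| Insertions | 1 | 2 |

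The first two scores show a halving with no fewer catheter-days. The next two show no change. Insertions move against the tag.

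**Step 2: averaged over a phase, total catheter time unchanged.** Let e be the excess of re-insertions over control, as a share of catheters. The documents give no rate, so 2% to 10% is an assumed range. The same catheter-days are spread over (1 + e) catheters, so the per-catheter mean falls by 1 − 1/(1 + e):

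- e = 0.02: 1 − 1/1.02 = 2.0%
- e = 0.05: 1 − 1/1.05 = 4.8%
- e = 0.10: 1 − 1/1.10 = 9.1%

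For scale, the Sample size section targets a fall from 50% to 40% in situ at day 4. If durations were exponential (an assumption; Data analysis anticipates normality), the means would be −4/ln(0.5) = 5.77 and −4/ln(0.4) = 4.37 days, a fall of about 24%.

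**Step 3: a real shortening together with some reversals.** Take a baseline of 4 days (the stated median, used here as a mean). The first catheter is shortened by 0.5 day, and a share f is re-catheterised for r days. Both f and r are assumed. First-episode duration is 4 − 0.5. The total per patient is 4 − 0.5 + f·r. The per-catheter mean is that total divided by (1 + f).

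| f | r (days) | First episode | Per catheter | Total per patient |
|---|---|---|---|---|
| 5% | 1 | −12.5% | −15.5% | −11.3% |
| 10% | 2 | −12.5% | −15.9% | −7.5% |
| 20% | 3 | −12.5% | −14.6% | +2.5% |
| 30% | 3 | −12.5% | −15.4% | +10.0% |

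First-episode duration does not respond to re-insertion at all. The total per patient, and with it the utilisation ratio if patient-days are fixed, does respond. In the last two rows the duration scores show a clear benefit while catheter use has risen.

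**Step 4: would the insertion rate show it?** With 25% of admissions catheterised (Sample size), 5% re-insertion moves the rate from 25 to 25 × 1.05 = 26.25 per 100 admissions, and 10% moves it to 27.5. A modest fall in first insertions would cancel either change.

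**The case against.** The strongest case on the other side has five parts.

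- **Unit.** A reader might infer that the protocol specifies duration per catheter and so turns harm into efficacy. It does not. Catheter-days are described for each patient, the sample size is in patients, and the Data analysis section gives no unit. If days are summed per patient, the bias in Steps 1 and 2 is zero. This stands, and it makes the point conditional. It does not dispose of it, because follow-up is written to end at removal and no rule brings a later catheter back in.
- **Other outcomes.** A reader might infer that re-insertion goes entirely unmeasured. The Table 2 ratio counts days after re-insertion, and the insertion rate rises with each one. This also stands. But the only Objective 1 model described is for duration, and the insertion rate cannot separate repeat from first insertions.
- **Safety.** A reader might infer that patients are left out of safety altogether. The sections on adverse events and incidents are not limited to staff, so that reading fails. What remains is that the Safety section names staff only, and that event reporting has no re-insertion item and no planned comparison by phase.
- **Data.** A second catheter is seen only if the patient is identified again on a participating ward, and researchers hold de-identified records. The data are therefore not simply there for the taking; linkage has to be done at the hospital.
- **Analysis-plan detail.** The length of a merging window can be left to an analysis plan. The end of follow-up, the dependent variable and the scope of safety are stated in the protocol itself.

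**Conclusion.** The point holds in conditional form. If duration stops at first removal or is taken per catheter, a removal that has to be reversed counts as a shorter duration, in the tag's favour. The protocol's text allows both readings and gives no rule against them. The utilisation ratio in Table 2 is not affected. No outcome isolates re-insertion, and the Safety section is narrower than the protocol's own event collection.

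The size is illustrative: 2.0%, 4.8% or 9.1% off the per-catheter mean for excess rates of 2%, 5% or 10%. It rests on assumed rates, on total catheter time being unchanged, and on the rate being an excess over control, since re-insertions equally common in both phases would not bias the comparison in this way. The figures show what the wording permits. They do not show that a bias of this size will occur.

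**What to change.** 1. **Follow-up and duration.** Continue recording catheters in the same patient until discharge. In the duration analysis, total the catheter-days per patient within a ward phase, split at transfer as the Intervention section already provides. Alternatively, merge a removal and a re-insertion within a prespecified window into one episode.
2. **Re-insertion by phase.** Report the proportion of removals followed by re-insertion within that window, for control and intervention phases. Link catheters by hospital number in the hospital's local file before de-identification.
3. **Safety.** Extend the Safety section's evaluation to patients, in line with the sections on adverse events and incidents.

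These are changes to measurement and wording only; no rule for managing catheters is implied. Hospital number and insertion and removal times are already in Table 3, so the cost is continued recording after a first removal, a small amount of local linkage and some text. Re-insertions on non-participating wards would still be missed, and the report should say so.
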